7.2.7 Lost to Follow-up

All reasonable efforts must be made to locate participants to determine and report their ongoing status. This includes follow-up with persons authorized by the participant. Lost to follow-up is defined by the inability to reach the participant after a minimum of 3 documented phone calls, faxes or emails (not performed on the same day), as well as a lack of response by the participant to one registered mail letter. All attempts should be documented in the participant's medical records. If it is determined that the participant has died, the site will use permissible local methods to obtain the date and cause of death and as much other information as can be obtained, including post-mortem reports.

Data to be collected at subsequent visits will be considered missing.

7.2.8 End of Study Definition

A patient will have completed the study if the patient dies while on Treatment or in Follow-up. The cause of death will be documented in the eCRF.

Patients no longer required to be followed for survival are considered as having completed the study if 1 of the following events occurs: disease progression or death. Following the completion of the treatment and Safety Follow-up phases of the study, every effort should be made to follow-up all patients for their survival status until patient death or termination by the Sponsor.

The end of the study is defined as the date once all patients have completed the Follow-up period (i.e., 12 weeks after discontinuation).

7.2.9 Discontinuation of Study Drug

When a patient will discontinue study drug treatment, the date and reason for study drug discontinuation should be documented on the CRF, all remaining visits of that treatment cycle should be completed (without infusions and with only a single PK sample taken at applicable visits), and the patient should enter the Follow-up period. When a patient will be withdrawn from the study (during the Treatment or Follow-up period), all evaluations associated with that study visit should be performed and the date and reason for study discontinuation should be documented on the CRF. In addition, if more than 4 weeks since the last imaging-based response assessment have passed at the time of discontinuation, a final response assessment shall be done if feasible.

Following completion or discontinuation of the Treatment and/or Follow-up phases of the study, all patients will be followed (by phone) every 3 months to assess their survival status until patient death.

Continued treatment should occur for patients with a best overall response (BOR) of CR (patients with confirmed CR may be discontinued from treatment upon discussion between the Investigator, Medical Monitor, and Sponsor), partial response (PR), or stable disease until the first occurrence of either:

- Documented progressive disease by RECIST 1.1 – while reference is made to [Section 7.1.4](#) for treatment beyond progression considering the principles of iRECIST ([Seymour et al., 2017](#))
- Clinical deterioration suggesting that no further benefit from treatment is likely
- Patient meets permanent discontinuation criteria for study therapy due to meeting respective tolerability criteria
- Other intolerance to therapy requiring discontinuation according to the Investigator's opinion
- Requirement for another form of antineoplastic therapy as determined by the Investigator or
- Discontinuation resulting from protocol violation, withdrawal of consent, or lost to follow-up
- Termination of the study by the Sponsor
- Pregnancy
- Need for prohibited medication
- Lack of compliance with the study and/or study procedures (e.g., administration instructions, study visits)
- Patient is lost to follow-up

If any of the above situations apply, the patient is withdrawn from treatment and enters the Follow-up period. Consequently, the reason for discontinuation of NM21-1480 will be recorded in the eCRF. These reasons include:

- Radiographic disease progression
- Any progression or recurrence of any malignancy, or any occurrence of another malignancy that requires active treatment
- Any significant AE that compromises the patient's ability to participate in the study
- Patient's decision to discontinue the study treatment (A patient who discontinues treatment is normally expected to continue to participate in the study unless they specifically withdraw their consent to further participation in any study procedures and assessments)

- The Investigator or Sponsor determines it is in the best interest of the patient
- Death

7.2.10 Discontinuation of Study Sites

Study site participation may be discontinued if Sponsor or designee, the Investigator or IEC/IRB of the study site judges it necessary for medical or safety reasons consistent with applicable laws, regulations and GCP.

7.2.11 Discontinuation of Study

The study will be discontinued if Sponsor or designee, including through SMC recommendation, judges it necessary for medical, safety, or business reasons consistent with applicable laws, regulation and GCP.

7.2.12 Follow-up

All patients will be followed for survival until death after discontinuation of the Treatment and/or completion of Follow-up periods.

- Follow-up 1 to be scheduled within 30 days of the last visit.
- Safety Follow-up Visit 2 and Visit 3 are to be scheduled 60 days and 90 days after discontinuation, respectively after discontinuation.
- Following completion or discontinuation of the Treatment and/or Follow-up phases of the study, all patients will be followed (by phone) every 3 months to assess their survival status until patient death.

8 STUDY TREATMENT

Study treatment is defined as the investigational intervention intended to be administered to the study participant according to the study protocol.

8.1 Administration of Study Treatment(s)

Part A (Dose-Escalation)

NM21-1480 will generally be administered over approximately 60-90 minutes as a single IV infusion every 14 days for a total of 2 infusions per treatment cycle (4 weeks). Details on study drug administration can be found in the study Pharmacy Manual. The following escalating flat dose levels will be administered according to the BOIN design:

IV Administration of NM21-1480

Dose 1: 0.15 mg

Dose 2: 1.5 mg

Dose 3: 8 mg

Dose 4: 24 mg

Dose 5: 80 mg

Dose 6: 240 mg

Dose 7: 800 mg

Radiological (response) assessments are done every 8 weeks, i.e., 1 assessment cycle (at 8-Week Assessment, see [Table 7-1](#)).

Part A-2 (optional)

Part A of the study was formally completed on 23 May 2022 at which occasion, based on availability of at least 28-day safety data for all 25 patients evaluable for BOIN in Part A, the SMC determined that Part A did not technically identify a MTD and that even the highest dose level assessed in Part A (800mg flat dose) was considered a tolerated dose. However, based on the finding that some patients dosed at 24-240mg in Part A developed treatment-emergent ADAs leading to loss of exposure, while this was not observed at the 800mg dose level, a decision was taken to explore one higher dose level (1400mg flat dose, applying an approximately 14-day dosing interval) in up to 10 patients within Part A-2 in parallel to studying the 800mg dose level in Part B. The SMC, together with the Sponsor, may also choose to evaluate different (i.e., longer than 2-week) dosing intervals if supported by emerging Part A-2 data. Additional dose levels (i.e. doses other than 1400mg) or dosing intervals (i.e. other than biweekly) may in the future be studied within Part A-2 as well if emerging data from the ongoing study provide a rationale to do so.

Part B (Dose Expansion):

8.1.1 Duration of Treatment with Study Drug

There is no pre-specified maximal treatment duration. Treatment for a given patient shall be continued until there is confirmed disease progression by the Investigator or the patient meets any of the pre-specified conditions for discontinuation.

8.1.2 8-Week Assessment

In Part A, radiological assessments are conducted every 8 weeks, this period defines 1 assessment cycle (i.e., in the week prior to administration of NM21-1480 in all odd number treatment cycles [e.g., Cycles 3, 5, 7]). In the optional Part A-2 and in Part B, radiological assessments are conducted every 6 weeks for the first 24 weeks on treatment and every 8 weeks thereafter.

8.1.3 Radiological Assessment in the Follow-up Period

All patients who discontinue study treatment without radiologically documented disease progression will continue to receive radiological assessments until disease progression, patient withdraws informed consent, initiation of new anti-cancer treatment, lost to follow-up, death, or end of this study, whichever occurs first.

8.1.4 Re-initiation of Study Therapy for Patients in Follow-up Period

Patients that have been discontinued from treatment will not be allowed to be re-initiated with the IP. The only exceptions are treatment re-initiations in patients who were discontinued due to confirmed CR and thereafter recurrence or in patients following elective surgery provided that patients still meet the eligibility criteria. Re-initiation of treatment in this situation may be allowed following discussion between Investigator, Medical Monitor and Sponsor.

8.1.5 Dose Modification

In the case that an infusion cannot be administered at a scheduled visit, every attempt should be made to administer the infusion as soon as possible. Patients with infusion delays >35 days (i.e., 2 missed doses + 7 days in settings with intended biweekly dosing events) or >49 days (i.e., 2 missed doses + 7 days in settings with intended dosing events every three weeks) from the scheduled dosing should normally discontinue treatment and enter the Follow-up period with the exception of delays related to prophylactic vaccinations or after specific consultation and agreement between the Investigator and the Medical Monitor in settings where benefit/risk may justify continued study therapy (e.g., patient deriving clinical benefit who requires prolonged steroid taper for management of non-DLT irAEs). For more details of dose modification relevant to irAEs, please refer to [Appendix VI](#), (irAE management guidance for Investigators).

8.1.5.1 Dose Reduction

In Part A, dose may be reduced to the next lower pre-specified dose level of the BOIN design due to toxicity if deemed necessary by the Investigator after consultation with the Medical Monitor, specifically after occurrence of a DLT.

Only one dose reduction is allowed.

In general, tolerability issues in both Part A and Part B are to be addressed by dose withholding; however, dose reduction may be considered upon discussion with the Medical Monitor if deemed necessary as per the Investigator's assessment.

8.1.5.2 Dose Withheld

NM21-1480 will be withheld for any of the following treatment-emergent adverse events (TEAEs):

- Any Grade ≥ 2 TRAE, with the following exceptions:
 - Grade 2 TRAE fatigue, alopecia, skin rash or laboratory abnormalities do not require a treatment delay
- Any Grade 3 skin, TRAE
- Any Grade 3 TRAE laboratory abnormality, with the following exceptions for lymphopenia, AST, ALT, or total bilirubin or asymptomatic amylase or lipase:

- Grade 3 lymphopenia does not require dose delay
- If a patient has a baseline AST, ALT or total bilirubin that is within normal limits, delay dosing for treatment-related Grade ≥ 2 toxicity
- If a patient has baseline AST, ALT, or total bilirubin within the Grade 1 toxicity range, delay dosing for treatment-related Grade ≥ 3 toxicity
- Any Grade ≥ 3 treatment-related amylase or lipase abnormality that is not associated with symptoms or clinical manifestations of pancreatitis does not require dose delay. The Medical Monitor should be consulted for such Grade ≥ 3 amylase or lipase abnormalities
- Any AE, laboratory abnormality, or intercurrent illness which, in the judgement of the Investigator, warrants delaying the dose of study medication.
- Grade 2 TRAEs that recur shall be managed by dose modifications (changes in the infusion rate) and dose delays, and those that do not resolve to Grade 1 or less by the end of the next treatment cycle shall lead to permanent discontinuation of NM21-1480. Pre-planned dose level reductions are not allowed; however, interruptions in delivering the planned dose that results in an actual dose that is less than 90% of the planned dose is defined as dose reduction.

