Part A of the study was formally completed on 23 May 2022 at which occasion, based on availability of at least 28-day safety data for all 25 patients evaluable for BOIN in Part A, the SMC determined that Part A did not technically identify a MTD and that even the highest dose level assessed in Part A (800mg flat dose) was considered a tolerated dose. However, based on the finding that some patients dosed at 24-240mg in Part A developed treatment-emergent ADAs leading to loss of exposure, while this was not observed at the 800mg dose level, a decision was taken to explore one higher dose level (1400mg flat dose) in up to 10 patients within Part A-2 in parallel to studying the 800mg dose level in Part B. For safety evaluation of this single additional dose level, the target toxicity rate applied for BOIN in Part A ($\phi = 0.3$) will be applied. Initially, 6 patients will be dosed with 1400mg of NM21-1480 in Part A-2 and upon completion of the 28-day DLT evaluation period for these six patients, as per SMC call, an additional up to 4 patients may be enrolled at this dose level (to end up with a maximum of 10 patients to be exposed to 1400mg in Part A-2), applying the decision rules defined for BOIN as detailed in Table 10-2. Whenever after 6 patients have completed the 28-day DLT evaluation period at the 1400mg dose level, according to the BOIN decision rules, de-escalation from the 1400mg dose or elimination of

the 1400mg dose would be required, further enrollment into the dose level will be stopped. In such situation, ongoing patients who are tolerating the dose level may be continued at 1400mg flat dose unless the safety review mandates dose reduction in which case the dose may be reduced to 800mg or the patient may be discontinued from treatment based on discussion between the investigator and the Medical Monitor. If tolerability of the 1400mg dose allows for completion of the 28-day DLT evaluation period for 6-10 patients, the SMC will determine based on the BOIN decision rule guidance provided in Table 10-2 whether:

- The 1400mg dose level is considered a tolerable dose and technically not considered to represent the MTD because BOIN would recommend further dose escalation at this point (i.e. $\phi \leq 0.236$)
- The 1400mg dose level is considered a tolerable dose and to represent the MTD if $\phi > 0.236$ and $\phi \leq 0.3$
- The 1400mg dose level is not considered a tolerable dose (i.e. $\phi > 0.3$)

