8.3 Patient Compliance

The dosage, timing and mode of administration of study medication may not be changed. Any departures from the intended regimen must be recorded in the eCRF. Study medication accountability and patient compliance will be documented throughout the study/treatment periods using study-specific medication administration record forms. If a participant does not receive the scheduled dose, every effort should be made to administer the dose as soon as possible. Deviations from the intended regimen include:

- receiving unscheduled dose of study drug
- missing a dose
- receiving the incorrect dose

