9.2.4.3 Action Taken with Study Drug Due to AE

The action taken with study drug should be recorded using one of the following:

- None
- Study drug temporarily discontinued
- Study drug permanently discontinued
- Unknown/not applicable

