10.6.6 Adverse Events

Adverse events will be coded using the most current version of the MedDRA. Incidence tables will be presented for all AEs by maximum grade according to CTCAE v5.0. Adverse events, SAEs, TEAEs, TRAEs (i.e., assessed as at least possibly related to study drug by the Investigator), and AEs resulting in dose reduction, interruption, or discontinuation of study drug will be tabulated, as well as AEs leading to additional therapy. Dose-limiting toxicity will also be tabulated. Summaries for deaths on study will be provided by system organ class and preferred term. Adverse event of special interest for NM21-1480 will be identified according to the most recent case retrieval strategy prior to database lock. Such categories consist of 1 or more well defined safety events which are similar in nature and for which there is a specific clinical interest in connection with the study treatment. For each specific category, number and percentage of patients with at least 1 event will be reported. Additional analyses (including time to onset and duration) may also be performed for these events.

Adverse event of special interest do not require expedited reporting to the Sponsor unless the event(s) meets SAE reporting criteria ([Section 9.2.6](#)).

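### Dose-level reduction is permitted in some protocol sections and restricted in others, the term has two meanings, and the AE action list cannot supply the required table of AEs resulting in dose reduction

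*Protocol*

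**What the plan says.** Several protocol sections allow a lower dose level. Section 8.1.5.1 states "In Part A, dose may be reduced to the next lower pre-specified dose level of the BOIN design due to toxicity" and adds "Only one dose reduction is allowed". It makes withholding the general approach in Parts A and B, but leaves reduction open after discussion with the Medical Monitor. Section 7.2.5 covers Part A-2 patients still on 1400 mg after enrollment at that dose has stopped. If the safety review requires it, "the dose may be reduced to 800mg or the patient may be discontinued from treatment". Section 7.2.5.3 likewise foresees that a safety review may impose a reduction in Part B.

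Other sections restrict it. Section 8.1.5.2 says "Pre-planned dose level reductions are not allowed" and, in the same sentence, labels as a dose reduction any interrupted delivery that falls below 90% of the planned dose. Section 8.1.7, on infusion-related reactions, rules out reductions other than a slower rate. Section 8.3, on compliance, says "The dosage, timing and mode of administration of study medication may not be changed".

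On data, 9.2.4.3 asks for one of four actions: none, "Study drug temporarily discontinued", its permanent counterpart, or unknown/not applicable. Section 10.6.6 requires that "AEs resulting in dose reduction, interruption, or discontinuation of study drug will be tabulated". SAP 3.6.2 summarises only TEAEs leading to temporary or permanent discontinuation.

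**The concern.** Safety and tolerability is a primary objective in every part of the study, and a step down in dose for toxicity is a direct tolerability outcome. Two things are at stake.

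The first is conduct. Depending on which section a site consults, the same toxicity could lead to a step down or only to holding or stopping the drug. The same step down could then be treated as compliant or as a protocol deviation.

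The second is reporting. A count of dose reductions means little if the term covers both a lower assigned level and a partly delivered infusion. A required AE table is also at risk if the field that should supply it has no matching code.

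**Working it through.** The protocol and SAP give no figure to reproduce. The check sets the passages side by side, follows one hypothetical patient through the data, and sizes the one pooled group that is affected.

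**1. The dosing passages**

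| Protocol section | Setting | Effect |
|---|---|---|
| 8.1.5.1 | Part A | One step down allowed for toxicity |
| 8.1.5.1 | Parts A and B | Withholding first; reduction open after discussion |
| 7.2.5 | Part A-2, after enrollment at 1400 mg stops | 1400 to 800 mg allowed if the safety review requires it |
| 7.2.5.3 | Part B | Reduction foreseen if the safety review requires it |
| 8.1.5.2 | Within the bullet on recurrent Grade 2 treatment-related AEs | Pre-planned level reductions barred |
| 8.1.7 | Infusion-related reactions | Only a slower rate allowed |

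The word pre-planned could mean only reductions scheduled in advance. The protocol does not define it, and the sentence closes a rule on managing toxicity. What 8.1.5.1 permits is a move to a level fixed in advance. The text does not settle which meaning applies.

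**2. The two meanings**

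The 90% threshold cannot separate the two events by itself. Against the originally assigned dose, a step from 1400 to 800 mg gives 800/1400 = 57%. The Part A steps give 240/800 = 30%, 80/240 = 33%, 24/80 = 30%, 8/24 = 33%, 1.5/8 = 19% and 0.15/1.5 = 10%. Every step is below 90%. If the planned dose is reset to the new level, the ratio becomes 100% and the step is not caught. The interruption and volume fields in SAP 3.3.8 could tell the events apart, but no rule says to use them for this.

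**3. One patient followed through the data: 1400 to 800 mg because of an AE**

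- AE action (9.2.4.3): no code fits. If the next infusion is on time at 800 mg, the nearest choice is no action. If an infusion is held first, it is a temporary discontinuation.
- Table in 10.6.6: the reduction entry has no source code, so it is empty or depends on miscoding.
- Table in SAP 3.6.2: the patient appears if a dose was held and is absent otherwise.
- Exposure (10.6.4; SAP 3.3.8): the administered milligrams show the lower dose, and 10.6.4 asks for the reason for modification. Neither section specifies a link to the individual AE.
- SAP section 6: it says that limited data restrict the outputs, but does not mention this tabulation.

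**4. Group membership**

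SAP 3.1.1 shows Part A by dose level, Part A-2 in total and Part B by cohort. It adds a total of all patients in any part who received 800 mg. The patient above stays in the Part A-2 column but also meets the wording of the pooled total.

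Inputs: 9 evaluable patients at 800 mg in Part A (Protocol Table 10-5); 5 in B1, 5 in B7, 10 in B8 and 5 in A-2 (SAP section 6). Assuming every Part B patient received 800 mg, the pool is 9 + 5 + 5 + 10 = 29. Protocol 5.3.2 counts 26 exposed against 25 evaluable in Part A, so it could be 30.

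- One reduced A-2 patient added: 1/30 = 3.3% (or 1/31 = 3.2%).
- All five added, the upper limit: 5/34 = 14.7% (or 5/35 = 14.3%).

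**The case against.** The strongest reply is that the passages can be read together: nothing is scheduled in advance, withholding is the norm, and an exceptional step down follows consultation or safety review. That reading is available, so a reader who infers a flat ban set against a flat permission goes further than the text. It remains an interpretation that the protocol does not give.

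A reader might also take 8.3 as a prohibition. It does not work as one. Its sentence covers timing as well, so it would equally forbid the delays that 8.1.5 and 8.1.5.2 authorise. The same section requires departures from the regimen to be recorded.

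A reader might infer that a reduction would go unrecorded. Sections 8.3 and 10.6.4 and SAP 3.3.8 contradict that. What is missing is the link to the AE.

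A reader might size the problem as one patient in 5 or 10, that is 20% or 10% of a group. The SAP does not support this. A reduction in Part A-2 or Part B leaves the patient in the same displayed group, except possibly in the pooled 800 mg total.

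Finally, Protocol 10.1 lets the SAP modify the outlined methods, and SAP 3.6.2 matches the codes in 9.2.4.3. That stands, but SAP section 6 lists changes from the protocol and does not include this one.

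**Conclusion.** The point holds as an inconsistency that needs clarifying. The sections on reducing the dose level are not reconciled, one term names two events, and the 10.6.6 tabulation cannot be derived from the action-taken field in 9.2.4.3. The SAP drops that tabulation without declaring it.

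The consequences are bounded. The documents record no reduction as having occurred, and no sample size or decision rule depends on the matter. The pooled 800 mg total could shift by about 3% per reduced Part A-2 patient, and by about 15% in the limiting case of all five.

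This rests on 9.2.4.3 being the list actually used, since the eCRF itself is not among the documents. The pooled figures also assume that Part A evaluable counts stand in for treated counts and that all 20 Part B patients received 800 mg. No view is taken on which dosing rule is right.

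**What to change.** 1. Reconcile Protocol 7.2.5, 7.2.5.3, 8.1.5.1, 8.1.5.2 and 8.1.7, with a cross-reference in 8.3, into one statement of whether and in which parts a dose-level reduction may occur. The clinical choice is the sponsor's.
2. Give the infusion delivered below 90% of plan its own name.
3. If reductions remain possible, add a dose-reduced code to 9.2.4.3 so that it matches 10.6.6. Otherwise, declare in SAP section 6 that the tabulation is dropped or is derived from exposure data. Simply deleting the 10.6.6 item would not be sound: under the definition in 8.1.5.2 it has content even if level reductions are barred.
4. State in the SAP whether a patient reduced from 1400 to 800 mg counts in the pooled 800 mg total, and flag such patients.

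The cost is a protocol clarification, one code on the AE form and a few lines in the SAP, with no effect on sample size. SAP section 4 reports early closure, so a new AE code may come too late for patients already treated. The SAP changes can still be made, because SAP section 1 has the plan finalised before database lock.
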